8.3.4 Modified Sartorius Score

The Sartorius scale was created as a more detailed and dynamic HS severity scale and was modified in order to further develop and simplify this assessment for the clinical setting (Sartorius et al, 2003; Sartorius et al, 2009; Sartorius et al, 2010). The Modified Sartorius Score was the first disease specific instrument for dynamically measuring clinical severity.

The Modified Sartorius Score includes an assessment of the anatomical regions involved, the numbers and types of lesions in each anatomical region, the longest distance between 2 relevant lesions within an anatomical region (or size of a single lesion), and whether all relevant lesions are separated by normal skin (yes or no). [Table 14–2](#) shows the scoring for each criterion.

A Regional Modified Sartorius Score will be derived for each reported anatomical region as:

$$\begin{aligned} \text{Regional Modified Sartorius Score} = \\ \text{Region} + 4 \times \text{DT} + 2 \times \text{IN} + 1 \times \text{AB} + 1 \times \text{HYS} + 1 \times \text{NIN} + 1 \times \text{NDT} \\ + \text{Distance} + \text{Separate} \end{aligned}$$

where

- Region = 3 if any lesion is present in the anatomical region, 0 otherwise
- DT = number of draining tunnels (fistulas/sinus tracts) in the region
- IN = number of inflammatory nodules in the region
- AB = number of abscesses in the region
- HYS = number of hypertrophic scars in the region
- NIN = number of non-inflammatory nodules in the region
- NDT = number of non-draining tunnels (fistulas/sinus tracts) in the region
- Distance =
 - 0 if no lesions are present in the anatomical region
 - 2 if longest distance between 2 relevant lesions or diameter of a single lesion is < 50 mm
 - 4 if longest distance between 2 relevant lesions or diameter of a single lesion is ≥ 50 mm and ≤ 100 mm
 - 8 if longest distance between 2 relevant lesions or diameter of a single lesion is > 100 mm
- Separate = 0 if all relevant lesions are clearly separated by normal skin in the region, 6 otherwise

For the purpose of the Regional Modified Sartorius Score derivation, the left and right sides of the body (if applicable) will be treated as 1 anatomical region (ie, the lesion assessment data from both sides will be pooled). For the Region, Distance and Separate variables defined above, the following will apply:

- Region: a value of 3 will be applied if at least 1 lesion is present in either the left or right sides of an anatomical region; if 1 or more lesions are present in both left and right sides of the body, this will still be scored as 3 for the region overall
- Distance: a score will be determined for each side of the body according to the scoring system above and the maximum of these scores will be used
- Separate:
 - if both left and right sides have relevant lesions separated by normal skin then this will be scored as 0;
 - if only one of the left and right sides have relevant lesions separated by normal skin, then this will be scored as 6

- if both left and right sides have no relevant lesions separated by normal skin then this will be scored as 6

The overall Modified Sartorius Score for a subject will then be calculated by summing the Regional Modified Sartorius Scores across all anatomical regions.

The Regional Modified Sartorius Score together with the overall Modified Sartorius Score will be listed by treatment group, subject and visit, including the change from Baseline for the overall Modified Sartorius Score. The observed overall Modified Sartorius Score and the changes from Baseline in the overall Modified Sartorius Score will be summarized by treatment group and visit. This summary will also be produced by Baseline Hurley Stage.

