9.3 Lesion count

The lesion count is defined as a broad assessment of all the various skin “appearances” that are termed “lesions” in HS subjects. The lesion count must address all relevant anatomical regions in each subject. The lesion count will include the following:

- Abscesses (circumscribed collection of purulent exudate frequently associated with swelling and other signs of inflammation, such as fluctuance, tenderness and pain)
- Non-inflammatory fistulas (a fistula is a pathologic passageway connecting to the skin surface from dermis or sc tissue. A non-inflammatory fistula is a non-tender or minimally tender, non-erythematous fistula.)
- Draining fistulas (fistulas that drain serous or purulent fluid, either spontaneously or by gentle palpation)
- Fistulas/sinus tracts (a fistula with sinus tracts is a pathologic passageway that has developed into a channel to the skin surface)
- Non-inflammatory nodules (non-tender or minimally tender, non-erythematous nodules)
- Inflammatory nodules (a tender, erythematous, well-defined nodule. The lesion has no evidence of fluctuance. A pyogenic granuloma lesion is considered an inflammatory nodule; a papule or pustule is not considered an inflammatory nodule.)
- Hypertrophic scars (enlargement or overgrowth of a scar so that it extends above the surrounding skin surface)
- Hurley Stage assessment (see [Section 9.9](#))

The longest distance between 2 relevant lesions (if only one lesion, measure diameter of lesion) and whether the lesions are clearly separated by normal-appearing skin (yes/no) will be measured.

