2.2.1.2 Exploratory efficacy variables

The exploratory efficacy variables are listed below and will be evaluated at scheduled visits in accordance with the schedule of assessments.

- Proportion of subjects with a total abscess and inflammatory nodule count of 0, 1, or 2 at Week 12
- Proportion of subjects with at least a 30% reduction and at least 1-unit reduction from Baseline in the Patient's Global Assessment (PGA) of Skin Pain (based on the subject's worst pain over the previous 24 hours) at Week 12
- Change from Baseline in Modified Sartorius Score at Week 12
- Change and percentage change from Baseline in lesion count (abscess count, inflammatory nodule count, abscess and inflammatory nodule count, and draining fistula count) over time
- Change from Baseline in International Hidradenitis Suppurativa Severity Scoring System (IHS4) score over time
- Change from Baseline in erythema assessment over time
- Change from Baseline in Hurley Stage over time
- Change and percentage change from Baseline in PGA of Skin Pain (pain at its worst and pain on average over the last 24 hours) over time
- Change from Baseline in the HS-Physician's Global Assessment 6-point scale over time
- Change from Baseline in the Dermatology Life Quality Index (DLQI) score over time
- Change from Baseline in European Quality of Life-5 Dimensions-3 Level questionnaire (EQ-5D-3L) (index and visual analogue scale [VAS] scores) over time
- Change from Baseline in Hospital Anxiety and Depression Scale (HADS), HADS-Anxiety (HADS-A) and HADS-Depression (HADS-D) scores over time

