8 EFFICACY ANALYSES

8.1 Lesion count assessment

The primary efficacy variable and some of the exploratory efficacy variables discussed in [Section 8.3](#) (IHS4, Modified Sartorius Score, HS-Physician's Global Assessment, Hurley Stage and Erythema assessment) are based on the assessment and/or counts of different types of lesions in the following main anatomical regions at each visit.

- Inguinal (groin)
- Axillary (armpit)
- Submammary and/or intermammary in women
- Gluteal
- Other

These anatomical regions are further classified into the following locations, for the left and right sides of the body, as applicable:

- Inguinal (groin) excluding genital and pubic area – Left, Right
- Inguinal (groin) including genital and pubic area – Left, Right
- Axillary (armpit) – Left, Right
- Submammary – Left, Right
- Intermammary
- Gluteal – Buttocks – Left, Right
- Gluteal – Perianal/Perineal

All “Other” anatomical regions with lesions present will be specified in free text on the eCRF. Note that investigators will be asked to only select ‘Other’ regions with more severe lesions present.

The number of each of the following types of lesions (classified as relevant or non-relevant) will be recorded in each anatomical region, and then summed across all anatomical regions:

Relevant Lesions:

- Abscesses
- Draining tunnels (fistulas/sinus tracts)
- Inflammatory nodules

Non-relevant Lesions:

- Non-draining tunnels (fistulas/sinus tracts)
- Non-inflammatory nodules
- Hypertrophic scars

If there are 2 or more relevant lesions present in an anatomical region, the longest distance between 2 relevant lesions will be recorded and an assessment of whether these 2 relevant lesions are clearly separated by normal skin will be made.

If only 1 lesion is present in an anatomical region, then the diameter of the single lesion will be recorded.

In addition to the lesion count data, the degree of erythema will be assessed for each anatomical region and scored as follows:

- 0 = No redness
- 1 = Faint but discernible pink coloration
- 2 = Moderate red coloration
- 3 = Very red or bright red coloration

The worst overall erythema score across all anatomical regions will then be derived automatically in the database and used in the analyses.

Hurley Stage (I, II and III) will also be recorded for each anatomical area and the worst overall Hurley Stage across all anatomical regions will then be derived automatically in the database and used in the analyses.

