14.2 Modified Sartorius Score

The scoring system for the presence, counts and measurements of relevant lesions by type are given in [Table 14-2](#).

Table 14-2: Modified Sartorius Score

Characteristics of HS lesions	Points
Anatomical region	
Any	3
None	0
Types of lesions	
Fistula ^a	4
Nodule ^b	2
Abscess	1
Scar ^c	1

Table 14–2: Modified Sartorius Score

Characteristics of HS lesions	Points
Other ^d	1
Total area involved^e	
< 5 cm	2
5 to 10 cm	4
> 10 cm	8
Are all lesions clearly separated by normal skin?^f	
Yes	0
No	6

HS=hidradenitis suppurativa

Taken from <http://cursoenarm.net/UPTODATE/contents/mobipreview.htm?36/33/37400> and adapted from:

^a Fistula includes draining tunnels (fistulas/sinus tracts)

^b Nodule refers to inflammatory nodules

^c Scar refers to hypertrophic scars

^d Other includes non-inflammatory nodules and non-draining tunnels (fistulas/sinus tracts).

^e Area is defined as the longest distance between 2 relevant lesions (ie, abscess, draining tunnel (fistula/sinus tract) or inflammatory nodule). If there is only 1 lesion it is the measurement of the single lesion diameter.

^f This refers to all relevant lesions.

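### SAP 8.3.4 gives conflicting rules for the *Separate* item of the Modified Sartorius Score: read literally, the left/right rules add 6 points when one side of a paired region has cleared

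*SAP*

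**What the plan says.** SAP 8.3.4 builds a regional score from Region, weighted lesion counts, Distance and *Separate*, and sums it over regions. For this purpose "the left and right sides of the body (if applicable) will be treated as 1 anatomical region", and the item is defined as "Separate = 0 if all relevant lesions are clearly separated by normal skin in the region, 6 otherwise". Table 14-2 in SAP 14.2 puts the same question, "Are all lesions clearly separated by normal skin", with 0 points for yes and 6 for no. Its footnote restricts the scope: "This refers to all relevant lesions".

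SAP 8.3.4 then gives three rules for combining the sides. *Separate* is 0 if both sides have separated relevant lesions. For the next case, "if only one of the left and right sides have relevant lesions separated by normal skin, then this will be scored as 6". It is also 6 if neither side has separated relevant lesions. No rule is given for a side that has no relevant lesions.

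Two passages bear on how the item is recorded. SAP 8.1 places it under a condition: "If there are 2 or more relevant lesions present in an anatomical region, the longest distance between 2 relevant lesions will be recorded", followed by the separation question for those two lesions. Protocol 9.3 has no such condition: "whether the lesions are clearly separated by normal-appearing skin (yes/no) will be measured".

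The variable affected is "Change from Baseline in Modified Sartorius Score at Week 12", listed as exploratory in SAP 2.2.1.2.

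**The concern.** When one side of a paired region has only separated lesions and the other side has none, all relevant lesions in the pooled region are separated. The definition and Table 14-2 therefore give 0. The side rules, taken at their word, give 6, because only one side has separated relevant lesions.

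This pattern arises whenever treatment clears one side of a region, which is an improvement the score should register. Protocol Table 5-1 schedules the score only at Baseline and Week 12, so the result is a single difference with no intermediate visits to expose an artefact. Two programmers could each follow a different part of SAP 8.3.4 and report different changes from the same data.

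**Working it through.** **Step 1: compare the rules.** Give each side one of three states: no relevant lesions, all separated, or not all separated. The nine left/right combinations score as follows, with mirror images merged.

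| Sides | Pooled definition and Table 14-2 | Side rules, literal |
|---|---|---|
| separated / separated | 0 | 0 |
| separated / not separated (2 combinations) | 6 | 6 |
| not separated / not separated | 6 | 6 |
| none / not separated (2 combinations) | 6 | 6 |
| none / separated (2 combinations) | **0** | **6** |
| none / none | **0** | **6** |

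The rules agree in 6 of 9 combinations and differ in 3. Each difference involves a side without relevant lesions. For none / none, the pooled 0 holds only vacuously, and the case matters only if the region is still reported.

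**Step 2: effect on the score.** The weights are from SAP 8.3.4: Region 3 if any lesion is present, 2 per inflammatory nodule, Distance 2 if under 50 mm, and *Separate* 0 or 6. Assumptions: inflammatory nodules only, all separated, no non-relevant lesions, and distance under 50 mm at both visits. With n nodules on each side:

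- Baseline, both rules: 3 + 2(2n) + 2 + 0 = 5 + 4n
- One side cleared, pooled: 3 + 2n + 2 + 0 = 5 + 2n, a change of −2n
- One side cleared, literal: 3 + 2n + 2 + 6 = 11 + 2n, a change of 6 − 2n

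| Nodules (left + right) | Baseline | Week 12 literal (change) | Week 12 pooled (change) |
|---|---|---|---|
| 2+2 to 2+0 | 13 | 15 (+2) | 9 (−4) |
| 3+3 to 3+0 | 17 | 17 (0) | 11 (−6) |
| 4+4 to 4+0 | 21 | 19 (−2) | 13 (−8) |

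The literal score rises when the lesion and Distance points lost in the region total less than 6. Otherwise the improvement is understated by 6. If Distance also falls from 4 to 2 in the 2+2 to 2+0 case, Baseline is 3 + 8 + 4 = 15. Week 12 is then 15 under the literal rules (change 0) and 9 under the pooled definition (change −6).

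**Step 3: other patterns, same assumptions.**

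- Worsening from 2+0 to 2+2: literal 15 to 13 (−2); pooled 9 to 13 (+4).
- A 2+0 region clears and is no longer reported: literal −15; pooled −9.
- One side empty at both visits, 3+0 to 2+0: literal 17 to 15, pooled 11 to 9; −2 under both, so no false change.

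**Step 4: reach.** SAP 8.1 lists five locations with a left and a right side. If each is scored as its own region, which is an assumption, the gap at one visit is at most 5 × 6 = 30 points.

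**The case against.** The strongest reply is that the side rules merely implement the definition above them and are meant for regions with relevant lesions on both sides. On that reading, only one side separated means that the other side's lesions are not separated, and all three places agree. The text allows this reading but does not state it. The neighbouring rules do cope with one-sided disease: Region scores 3 for a lesion on either side, and Distance takes the larger of the two side scores, with 0 for an empty side. Even on the charitable reading, a cleared side has no rule of its own. Neither the amendment list in SAP 15 nor the list of changes in SAP 3.9 mentions this derivation.

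Some narrower points stand:

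- SAP 8.3.4 does not say whether a region is a main anatomical region or one of the finer locations in SAP 8.1, so the count of five pairs is conditional.
- Neither the definition nor Table 14-2 says explicitly how 0 or 1 relevant lesion is scored; giving 0 is a convention. A side with a single lesion may also draw the 6, depending on how the item is recorded.
- SAP 8.1 records separation for the two lesions furthest apart, which need not describe every lesion on a side with three or more. The pooled definition already has this limit.
- The examples are single regions with assumed counts. A reversal in one region need not reverse the overall score, and the documents do not show how often one side clears.

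**Conclusion.** The concern holds. As written, SAP 8.3.4 contains two rules for *Separate* that give different scores when one side of a paired region has only separated relevant lesions and the other has none. The difference is 6 points per affected region at a visit. In the simplest example it turns a change of −4 into +2. The sizes rest on the assumed lesion patterns.

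The consequence is limited. The variable is exploratory and summarized descriptively, and neither HiSCR nor the success criterion uses this item. The errors run in both directions, so no net bias between arms is claimed. The correction should be made because the rule as stated can score an improvement as a worsening.

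**What to change.** Replace the three side rules for *Separate* in SAP 8.3.4 with one: score 6 only if at least one side has two or more relevant lesions that are not clearly separated by normal skin; score 0 otherwise, including for sides or regions with no relevant lesion or only one. This matches the pooled definition and Table 14-2 where they speak, and states a convention for 0 or 1 lesion where they do not.

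Before database lock this needs a SAP amendment, as SAP section 1 requires for a changed analysis definition. After lock, describe the rule used and the reason in the CSR. The cost is a few lines of text and derivation code plus that entry. It uses the lesion counts and separation item already collected, and asks no more of them than the pooled definition does.

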8.3.5 Hidradenitis Suppurativa Physician's Global Assessment – Derived

The HS-Physician's Global Assessment is a validated 6-point scale that is used to measure improvement in inflammatory nodules, abscesses, and draining fistulas (Kimball et al, 2012; Zouboulis et al, 2015). The HS-Physician's Global Assessment scale is defined in [Section 14.1](#).

The scale ranges from "Clear" (no inflammatory or non-inflammatory nodules) to "Very severe" (more than 5 abscesses or draining fistulas). The gradings will be derived on a subject-level basis (ie, across all anatomical regions) based on the following rules:

- Clear:
 - number of abscesses = 0;
 - number of draining tunnels (fistulas/sinus tracts) = 0;
 - number of inflammatory nodules = 0;
 - number of non-inflammatory nodules = 0;
 - number of non-draining tunnels (fistulas/sinus tracts) – no limit;
 - number of hypertrophic scars – no limit;
- Minimal:
 - number of abscesses = 0;
 - number of draining tunnels (fistulas/sinus tracts) = 0;
 - number of inflammatory nodules = 0;
 - number of non-inflammatory nodules ≥ 1 ;
 - number of non-draining tunnels (fistulas/sinus tracts) – no limit;
 - number of hypertrophic scars – no limit;
- Mild:
 - number of abscesses = 0;
 - number of draining tunnels (fistulas/sinus tracts) = 0;
 - number of inflammatory nodules ≥ 1 and ≤ 4 ;
 - number of non-inflammatory nodules – no limit;

- number of non-draining tunnels (fistulas/sinus tracts) – no limit;
- number of hypertrophic scars – no limit;

OR

- sum of number of abscesses and number of draining tunnels (fistulas/sinus tracts) = 1;
- number of inflammatory nodules = 0;
- number of non-inflammatory nodules – no limit;
- number of non-draining tunnels (fistulas/sinus tracts) – no limit;
- number of hypertrophic scars – no limit;

- Moderate:

- number of abscesses = 0;
- number of draining tunnels (fistulas/sinus tracts) = 0;
- number of inflammatory nodules ≥ 5 ;
- number of non-inflammatory nodules – no limit;
- number of non-draining tunnels (fistulas/sinus tracts) – no limit;
- number of hypertrophic scars – no limit;

OR

- sum number of abscesses and number of draining tunnels (fistulas/sinus tracts) = 1;
- number of inflammatory nodules ≥ 1 ;
- number of non-inflammatory nodules – no limit;
- number of non-draining tunnels (fistulas/sinus tracts) – no limit;
- number of hypertrophic scars – no limit;

OR

- sum of number of abscesses and number of draining tunnels (fistulas/sinus tracts) ≥ 2 and ≤ 5 ;
- number of inflammatory nodules ≤ 10 ;
- number of non-inflammatory nodules – no limit;
- number of non-draining tunnels (fistulas/sinus tracts) – no limit;
- number of hypertrophic scars – no limit;

- Severe:

- sum of number of abscesses and number of draining tunnels (fistulas/sinus tracts) ≥ 2 and ≤ 5 ;
- number of inflammatory nodules > 10 ;

- number of non-inflammatory nodules – no limit;
- number of non-draining tunnels (fistulas/sinus tracts) – no limit;
- number of hypertrophic scars – no limit;
- Very Severe:
 - sum of number of and number of draining tunnels (fistulas/sinus tracts) > 5;
 - number of inflammatory nodule – no limit;
 - number of non-inflammatory nodules – no limit;
 - number of non-draining tunnels (fistulas/sinus tracts) – no limit;
 - number of hypertrophic scars – no limit

The HS-Physician's Global Assessment will be listed by treatment group and subject at each visit. The number and percentage of subjects at each level of the assessment scale (Clear, Minimal, Mild, Moderate, Severe and Very severe) will be presented by treatment group, visit, overall and by Baseline Hurley Stage. The denominator for the percentages will be based on the number of subjects in the given treatment group, Baseline Hurley Stage and visit for which there are no missing data for the HS-Physician's Global Assessment.

Shift tables for the changes from Baseline in this scale will be presented for each post-Baseline visit by treatment group, overall and by Baseline Hurley Stage. The denominator for the percentages will be based on the number of subjects in the given treatment group, Baseline Hurley Stage and visit for which there is no missing data for the change from Baseline in HS-Physician's Global Assessment

8.3.6 Dermatology Life Quality Index

The DLQI is a questionnaire designed for use in adult subjects with inflammatory skin diseases and has been used in patients with HS (Finlay, 1998; Esmann et al, 2010; Basra et al, 2012). The DLQI is a skin disease specific questionnaire aimed at the evaluation of how symptoms and treatment affect subjects' health related quality of life (QoL).

This instrument asks subjects about symptoms and feelings, daily activities, leisure, work and school, personal relationships and treatment. The total DLQI score ranges from 0 to 30 with higher scores indicating lower health related QoL. The complete questionnaire is shown in [Section 14.3](#) together with the scoring and derivation of the total DLQI.

Each question on the DLQI will be listed by treatment group and subject for each visit. The listing will also include the total DLQI score at each visit together with the changes from Baseline in the total DLQI score. Summary statistics will be presented for the observed total DLQI score at each visit together with the changes from Baseline in the total DLQI score by treatment group, overall and by Baseline Hurley Stage.

The number and percentage of subjects with a total DLQI score in each of the following categories will be summarized at each visit, by treatment group, overall and by Baseline Hurley Stage:

- Total DLQI score of 0 or 1

- Change from Baseline in the total DLQI score of -4 or below

For the summary of the change from Baseline in the total DLQI score of -4 or below, the denominator for the percentages will be the number of subjects with non-missing data and who had a total DLQI score of 4 or higher at Baseline.

